6. STUDY TREATMENTS

6.1. Part A

The study treatment names and ordering to be used in the TFLs for Part A are presented in [Table 1](#). The study treatment sequence names and ordering to be used in the TFLs for Part A are presented in [Table 2](#).

Table 1: Presentation of Study Treatments in TFLs (Part A)

Group	Study Treatment	Order in TFLs
A1 to A8	Placebo ^a	1
A1	1 mg KRP-A218 (Fasted Male)	2
A2a	3 mg KRP-A218 (Fasted Male)	3
A2b	3 mg KRP-A218 (Fed Male)	4
A3	3 mg KRP-A218 (Fasted Female)	5
A4	6 mg KRP-A218 (Fasted Male)	6
A5	12 mg KRP-A218 (Fasted Male)	7
A6 ^b	24 mg KRP-A218 (Fasted Male)	8
A7 ^b	XX mg KRP-A218 (Fasted Male)	9
A8 ^b	XX mg KRP-A218 (Fasted Male)	10
	XX mg KRP-A218 (Fasted Male)	11

^a Placebo will be pooled across all groups, regardless of sex and the fasting condition

^b Optional group, to be included if required

Table 2: Presentation of Study Treatment Sequences in TFLs (Part A; Food-effect Group Only)

Group	Study Treatment Sequence	Order in TFLs
A2a	Placebo (Fasted Male) / Placebo (Fed Male)	1
A2a	3 mg KRP-A218 (Fasted Male) / 3 mg KRP-A218 (Fed Male)	2

All TFLs will be based on actual treatments (eg, if subject was assigned to receive placebo but was wrongfully dosed with active treatment they would be summarised and listed under active treatment).

All dose levels described above are the potential dose levels, and therefore are subject to change. The TFLs will reflect the dose levels utilised in the study, and these will be displayed in increasing order.

All fasting conditions described above are the potential fasting conditions, and therefore are subject to change. The TFLs will reflect the fasting conditions utilised in the study.

The food-effect group described above is the potential food-effect group, and therefore is subject to change. The TFLs will reflect the food-effect group utilised in the study.

The sex-effect group described above is the potential sex-effect group, and therefore is subject to change. The TFLs will reflect the sex-effect group utilised in the study.

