Overall, 48 subjects will be studied in 5 groups (Groups A1 to A5); Groups A1, and A3 to A5 will consist of 8 male subjects, and Group A2 will consist of 16 subjects split into 2 subgroups (Group A2a [male subjects only] and Group A2b [female subjects only]) that will consist of 8 subjects each.

Potential subjects will be screened to assess their eligibility to enter the study within 28 days prior to the first dose administration. Each subject will participate in 1 treatment period only, except for Group A2a, where each subject will participate in 2 treatment periods where doses of KRP-A218 will be separated by an interval of 7 to 10 days (up to and including Day -1 of Treatment Period 2). The washout period may be extended depending on the observed apparent terminal elimination half-life ($t_{1/2}$) of CCI [REDACTED]. Subjects will reside at the study site from Day -1 (the day before dosing) to Day 4 of each treatment period.

All subjects will return for a follow-up visit 7 to 10 days after their final dose. The follow-up period may be extended depending on the observed $t_{1/2}$ of CCI [REDACTED]. In each of Groups A1, A2a, A2b, and A3 to A5, 6 subjects will receive KRP-A218 and 2 subjects will receive placebo. In Groups A1, A2b, and A3 to A5, all doses will be administered in the fasted state on the morning of Day 1. For Group A2a, Period 1, Day 1 doses will be administered in the fasted state and Period 2, Day 1 doses will be given 30 minutes after starting a standard high-fat breakfast. Each subject in Groups A1, A2b, and A3 to A5 will receive only a single dose of KRP-A218 or placebo during the study. In Group A2a, subjects will have the same treatment in both periods, such that each subject will receive 2 single doses of KRP-A218 or placebo during the study.

All groups in Part A (with the exception of Group A2a in Treatment Period 2) will receive the investigational medicinal product (IMP) using a sentinel approach. For each group, 2 subjects (1 KRP-A218 and 1 placebo) will receive the IMP at least 24 hours before the remaining subjects.

Part B:

There will be 4 groups, consisting of male subjects. Part B may overlap with Part A.

Overall, 40 subjects will be studied in 4 groups (Groups B1 to B4), with each group consisting of 10 male subjects. Part B may start after completion of Group A3, at dose equal to or less than given in Groups A1 to A3.

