4. STUDY DESIGN

4.1. Part A (Single Ascending Dose Study)

Part A will comprise a double-blind, randomised, placebo-controlled, single-dose, sequential-group, escalating-dose study incorporating a single-group, 2-period arm to investigate the effect of food on the PK of CCI. Part A will also include a sex-effect arm (Groups A2a and A2b) which will investigate the effect of sex on PK of CCI by comparing PK parameters following dosing in females versus dosing in males. Overall, 48 subjects will be studied in 5 groups (Groups A1 to A5); Groups A1, and A3 to A5 will consist of 8 male subjects, and Group A2 will consist of 16 subjects split into 2 subgroups (Group A2a [male subjects only] and Group A2b [female subjects only]) that will consist of 8 subjects each.

Potential subjects will be screened to assess their eligibility to enter the study within 28 days prior to the first dose administration. Each subject will participate in 1 treatment period only, except for Group A2a, where each subject will participate in 2 treatment periods where doses of KRP-A218 will be separated by an interval of 7 to 10 days (up to and including Day -1 of Treatment Period 2). The washout period may be extended depending on the observed $t_{1/2}$ of CCI. Subjects will reside at the study site from Day -1 (the day before dosing) to Day 4 of each treatment period.

All subjects will return for a follow-up visit 7 to 10 days after their final dose. The follow-up period may be extended depending on the observed $t_{1/2}$ of CCI [REDACTED]

Based on the ongoing review of the safety, tolerability, and PK results, additional nonresidential visits may be required. The number of additional visits per subject will not exceed 3 per period (as applicable) and will not extend beyond 28 days after each final dosing occasion. All subjects may stay in the clinical research unit (CRU) outside treatment periods due to coronavirus disease 2019 (COVID-19) risks.

[figure not shown]

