In each of Groups A1 to A5, 6 subjects will receive KRP-A218 and 2 subjects will receive placebo in accordance with a randomisation schedule. In Groups A1, A2b, and A3 to A5, all doses will be administered in the fasted state on the morning of Day 1. For Group A2a, Period 1, Day 1 doses will be administered in the fasted state and Period 2, Day 1 doses will be given 30 minutes after starting a standard high-fat breakfast. Each subject in Groups A1, A2b, and A3 to A5 will receive only a single dose of KRP-A218 or placebo during the study. In Group A2a, subjects will have the same treatment in both periods, such that each subject will receive 2 single doses of KRP-A218 or placebo during the study.

All groups in Part A (with the exception of Group A2a in Treatment Period 2) will receive the study treatment using a sentinel approach.

The total duration of study participation for each subject (from screening through follow-up visit) is anticipated to be up to 39 days (Groups A1, Group A2b [female subjects only], A3 to A5) or up to 50 days (Group A2a; male subjects only).

[figure not shown]
An overview of the study design is shown in [Figure 1](#) and [Figure 2](#), and the planned dose levels in [Figure 5](#).

Figure 1: Study Schematic (Part A; Groups A1, A2b [Female subjects Only], and A3 to A5)

*CRU = Clinical Research Unit

The follow-up period may be extended depending on the observed $t_{1/2}$ of CCI [REDACTED]

Figure 2: Study Schematic (Part A; Group A2a [Male subjects Only])

The washout and follow-up periods may be extended depending on the observed $t_{1/2}$ of CCI

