8.7. Safety and Tolerability Assessments

8.7.1. Adverse Events

All AEs will be coded using the Medical Dictionary for Regulatory Activities (MedDRA) Version 24.0 (or higher if a new version is issued during the study; see the DMP for more details).

A treatment-emergent adverse event (TEAE) will be defined as an AE that starts during or after the first dose, or starts prior to the first dose and increases in severity after the first dose.

A treatment-related TEAE will be defined as a TEAE with a relationship of possibly related or related to the study treatment, as determined by the investigator.

For Group A2a in Part A, the assignment of TEAEs to treatments will be as follows:

- A TEAE that starts or increases in severity during or after Period 1, Day 1 dosing and prior to Period 2, Day 1 dosing will be assigned to '3 mg KRP-A218 (Fasted Male)'.
- A TEAE that starts or increases in severity during or after Period 2, Day 1 dosing will be assigned to '3 mg KRP-A218 (Fed Male)'.

For Part C, the assignment of TEAEs to treatments will be as follows:

- A TEAE that starts or increases in severity during or after Day 1 dosing and prior to Day 4 dosing will be assigned to 'XX mg KRP-A218 Alone'.
- A TEAE that starts or increases in severity during or after Day 4 dosing and prior to Day 11 dosing will be assigned to '200 mg Itraconazole Alone'.
- A TEAE that starts or increases in severity during or after Day 11 dosing will be assigned to 'XX mg KRP A218 + 200 mg Itraconazole'.

All AEs will be listed. In addition to the data recorded in the database, the listings will include derived onset time and duration. Onset time will be calculated from the time of the last associated dose for TEAEs only. Where the last associated dose is referring to the last dose received prior to the start of a TEAE.

The frequency of subjects with TEAEs and the number of TEAEs will be summarised for the following categories:

- TEAEs (overall, serious, leading to discontinuation, and leading to death) by treatment
- TEAEs by severity and treatment
- Treatment-related TEAEs (overall, serious, leading to discontinuation, and leading to death) by treatment
- Treatment-related TEAEs by severity and treatment

The frequency of subjects will be summarised separately for TEAEs and treatment-related TEAEs by the following:

- System organ class, preferred term, and treatment
- Preferred term and treatment

For the AE data the following rules will apply:

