8.7.3. Vital Signs Parameters

All vital signs parameters and their changes from baseline will be listed; any value outside the clinical reference range will be flagged.

Summary tables and boxplots by treatment and timepoint for Parts A and B and by timepoint for Part C will be provided for all vital signs parameters and their changes from baseline.

8.7.4. 12-lead Electrocardiogram Parameters

All 12-lead ECG parameters and their changes from baseline will be listed; any value outside the clinical reference range will be flagged.

Summary tables and boxplots by treatment and timepoint for Parts A and B and by timepoint for Part C will be provided for all 12-lead ECG parameters and their changes from baseline.

An outlier analysis will be performed for QT interval corrected for heart rate using Fridericia's formula (QTcF). The analysis will include all individual original, repeat, and unscheduled postdose values.

The maximum postdose values will be summarised by treatment for all Parts according to the following categories:

- ≤ 450 ms
- >450 and ≤ 480 ms (all instances flagged in the listing)
- >480 and ≤ 500 ms (all instances flagged in the listing)
- >500 ms (all instances flagged in the listing)

The maximum increases from baseline will be summarised by treatment for all Parts according to the following categories:

- ≤ 30 ms
- >30 and ≤ 60 ms (all instances flagged in the listing)
- >60 ms (all instances flagged in the listing)

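### Pooling Part A placebo across fasting state gives two of the 12 placebo subjects two dosing occasions in one column, while active columns have one per subject: a small upward bias in placebo rates

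*SAP*

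**What the plan says.** - SAP 6.1, Table 1, footnote a: "Placebo will be pooled across all groups, regardless of sex and the fasting condition". This is an explicit rule. The column covers all groups, including any optional ones.
- Protocol synopsis, on allocation: "In each of Groups A1, A2a, A2b, and A3 to A5, 6 subjects will receive KRP-A218 and 2 subjects will receive placebo".
- SAP 4.1, on Group A2a: "subjects will have the same treatment in both periods, such that each subject will receive 2 single doses of KRP-A218 or placebo". Period 1 is fasted and Period 2 follows a high-fat breakfast.
- SAP Table 1 lists the A2a active data as two treatments, 3 mg fasted male and 3 mg fed male. The A2a rule in SAP 8.7.1 assigns adverse events to those two active labels only and does not mention placebo.
- SAP Table 2 has a sequence label that separates fasted from fed placebo in A2a, but does not say which outputs use it.
- SAP 8.7.1, on adverse events: "The frequency of subjects with TEAEs and the number of TEAEs will be summarised for the following categories". The categories are broken down by treatment.
- SAP 8.7.4, on QTcF outliers: "The maximum postdose values will be summarised by treatment for all Parts". Maximum increases from baseline are handled the same way.
- SAP 8.7.7 plans no inference on safety data.

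**The concern.** Safety and tolerability is the primary objective of Part A, and pooled placebo is its only control. With no tests planned, readers will compare the columns by eye, so the columns should be built alike.

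They are not. An A2a active subject appears in two columns with one occasion in each. An A2a placebo subject appears in one column with both. That subject's adverse-event window in the column is two intervals of 7 to 10 days (14 to 20 days in all) against one such interval for everyone else. The QTcF maximum is also taken over two rounds of safety ECGs, because the schedule in Protocol Appendix 6, Table 10 is repeated in Period 2. On a subject count, a second period can only add subjects with an event. The bias therefore raises the placebo rate and flatters the active columns.

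**Working it through.** **Inputs.** Six groups or subgroups (A1, A2a, A2b, A3, A4, A5) of 8 subjects, each with 6 active and 2 placebo (Protocol synopsis; SAP 4.1). A2a has two periods (SAP 4.1). The documents give no placebo event or outlier rate, so p, the chance that a subject has an event in one period, is assumed and varied.

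**The plan's own figure.** 6 × 8 = 48 subjects, as SAP 4.1 states. Of these 36 are active and 6 × 2 = 12 are placebo.

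**Dosing occasions on placebo.** 10 × 1 + 2 × 2 = 14 from 12 subjects, or 14/12 = 1.17 per subject. Every active column has exactly 1 per subject.

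**Expected incidence, subject denominator.** With equal and independent risk in the two periods, a twice-dosed subject has at least one event with probability 1 − (1 − p)² = 2p − p². Then

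[10p + 2(2p − p²)]/12 = p + p(1 − p)/6.

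| p per period | Pooled placebo | Excess (points) | Relative | Extra subjects of 12 |
|---|---|---|---|---|
| 0.02 | 0.0233 | 0.33 | 16.3% | 0.04 |
| 0.05 | 0.0579 | 0.79 | 15.8% | 0.10 |
| 0.10 | 0.1150 | 1.50 | 15.0% | 0.18 |
| 0.20 | 0.2267 | 2.67 | 13.3% | 0.32 |
| 0.30 | 0.3350 | 3.50 | 11.7% | 0.42 |
| 0.50 | 0.5417 | 4.17 | 8.3% | 0.50 |

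The excess peaks at p = 0.50, where 0.25/6 = 0.0417.

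**At least one event in the column.** At p = 0.05 the chance is 1 − 0.95¹² = 46.0% with one occasion each and 1 − 0.95¹⁴ = 51.2% as pooled.

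**Within-subject correlation ρ.** The excess becomes (1 − ρ)p(1 − p)/6. At p = 0.20 the pooled rate is 0.227 for ρ = 0, 0.213 for ρ = 0.5 and 0.200 for ρ = 1.

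**Different fed risk.** With fed risk p_f the pooled rate is p + p_f(1 − p)/6. At p = 0.20 it is 0.213 if the fed risk is half the fasted risk and 0.253 if it is double.

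**Optional groups.** Three more groups (Protocol 3.3) would give 18 placebo subjects. The excess is then p(1 − p)/9, at most 2.8 points.

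**Other denominator.** SAP 8.7.1 counts repeats of the same preferred term under the same treatment once. If such collapsed counts were divided by 14 subject-periods, the figure at p = 0.20 would be (10 × 0.20 + 2 × 0.36)/14 = 0.194, slightly below p. The direction therefore depends on the denominator.

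**Scale of chance variation.** The binomial standard error for 12 subjects, √[p(1 − p)/12], is 6.3 points at p = 0.05 and 11.5 points at p = 0.20. One subject is 8.3 points in a placebo column of 12 and 16.7 points in an active column of 6.

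**The case against.** The strongest reply is that this is too small to matter. The excess is well under the standard error, the relative figures assume fully independent periods, and no stated decision uses the placebo column. Escalation under Protocol 3.6 and 3.7 rests on review of the data and on individual or within-group criteria. The continuous ECG recordings for concentration-QTc exclude Period 2. All adverse events and ECG values are listed, so the two subjects can be inspected. All of this stands, and it sets the priority.

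A second reply is that the footnote fixes a display label, not a counting rule, and that the separate shells document for tables, figures and listings, which is not available here, may settle the counting. This stands in part. The pooling itself is written out and nothing in the SAP limits A2a placebo to one period. But the denominator is only implied for adverse events, where subjects are counted, and is not stated for QTcF.

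A reader might also infer more than the documents support:

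- **That n is 14 at each timepoint, with repeated subjects treated as independent.** The SAP does not say how two placebo values at one nominal time are handled. Section 8.1.2 describes n as a number of subjects, and no safety model or interval exists for which independence would matter.
- **That one in seven placebo readings at every timepoint is distorted by a meal.** Fasted subjects also eat from 4 hours after dosing (Protocol 6.2.1). Day 2 to 4 vital signs and ECGs are taken before breakfast in both periods (Protocol Appendix 6, Tables 9 and 10). Any contrast is mainly confined to the first hours after dosing, and the documents give no figure to size it.
- **That the fed state itself raises events.** Nothing shows this. The mechanism is the second observation period.

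**Conclusion.** The concern holds as a small bias built into the column definitions. Twelve planned placebo subjects bring 14 dosing occasions to one column, while each active column has one per subject. On a subject denominator, with equal and independent risk per period, expected placebo incidence is raised by p(1 − p)/6: 0.8 points at p = 0.05, 2.7 at p = 0.20 and never more than 4.2. Positive within-subject correlation shrinks the excess, to zero at correlation 1. For adverse events the subject denominator follows from the wording; for QTcF categories the result is conditional on counting per subject.

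The effect is to make active columns look slightly better in descriptive tables. It would be wrong to conclude that it could hide a safety signal of useful size or alter escalation: the excess is half a subject at most, and no stated rule refers to the placebo column. It is a cheap improvement of low priority.

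**What to change.** 1. In SAP Table 1, replace the single column with 'Placebo (Fasted)', pooled over all groups and both sexes and using only Period 1 for A2a. Set it beside the fasted active columns.
2. Show A2a Period 2 placebo as 'Placebo (Fed Male)', next to the fed 3 mg column. Table 2 already uses labels of this kind.
3. Extend the A2a assignment rule in SAP 8.7.1 to the two placebo labels, and state there and in 8.7.4 that denominators are subjects per column.

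Each subject then contributes one dosing occasion per column, and expected placebo incidence equals p. The fasted pool keeps all 12 planned placebo subjects.

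The cost is SAP and table-shell wording plus one column. The drawback is that the fed placebo column has n = 2. Under SAP 8.1.2 its continuous data would show only n, minimum and maximum, so it gives the fed active column little by way of a comparator.

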6.2. Part B

The study treatment names and ordering to be used in the TFLs for Part B are presented in [Table 3](#).

Table 3: Presentation of Study Treatments in TFLs (Part B)

Groups	Study Treatment	Order in TFLs
B1 to B7	Placebo ^a	1
B1	XX mg KRP-A218 (QD ^b)	2
B2	XX mg KRP-A218 (QD ^b)	3
B3	XX mg KRP-A218 (QD ^b)	4
B4	XX mg KRP-A218 (QD ^b)	5
B5 ^c	XX mg KRP-A218 (QD ^b)	6
B6 ^c	XX mg KRP-A218 (QD ^b)	7
B7 ^c	XX mg KRP-A218 (QD ^b)	8

Abbreviations: QD = once daily; BID = twice a day; TID = three times a day

^a Placebo will be pooled across all groups, regardless of sex, the fasting condition, or the dosing frequency

^b The planned dosing frequency is QD, however the dosing frequency may be changed following review of data from Part A (eg, to BID or TID)

^c Optional group, to be included if required

All TFLs will be based on actual treatments (eg, if subject was assigned to receive placebo but was wrongfully dosed with active treatment they would be summarised and listed under active treatment).

All dose levels described above are the potential dose levels, and therefore are subject to change. The TFLs will reflect the dose levels utilised in the study, and these will be displayed in increasing order.

If the fasting conditions vary across groups in Part B, then the active treatment labels will include the fasting status information (eg, 'XX mg KRP-A218 (QD) (Fasted)' or 'XX mg KRP-A218 (QD) (Fed)').

6.3. Part C

The study treatment names and ordering to be used in the TFLs for Part C are presented in [Table 4](#). The study treatment sequence name and ordering to be used in the TFLs for Part C are presented in [Table 5](#).

Table 4: Presentation of Study Treatments in TFLs (Part C)

Group	Study Treatment	Order in TFLs
C1	XX mg KRP-A218 Alone	1
	200 mg Itraconazole Alone	2
	XX mg KRP-A218 + 200 mg Itraconazole	3

Table 5: Presentation of Study Treatment Sequence in TFLs (Part C)

Group	Study Treatment Sequence	Order in TFLs
C1	XX mg KRP-A218 on Day 1; 200 mg Itraconazole (BID) on Day 4; 200 mg Itraconazole (QD) on Days 5 to 10; XX mg KRP-A218 + 200 mg Itraconazole (QD) on Day 11; 200 mg Itraconazole (QD) on Days 12 and 13	1

Abbreviations: QD = once daily; BID = twice a day

All TFLs will be based on actual treatment sequence. The 'Days X to Y' part of the treatment sequence labels will be kept unchanged even if a subject misses a dose on 1 or more days. Exact dosing regimen details including duration and days on which dose was received will be presented in the treatment administration listing only.

7. DEFINITIONS OF POPULATIONS

Any protocol deviations, including those due to COVID-19 and related restrictions (see [Section 8.1.1](#)), will be considered prior to database lock for their importance and taken into consideration when assigning subjects to populations.

7.1. All Subjects Population

The all subjects population will include all subjects who signed the informed consent form and had any study assessment recorded in the database per the protocol.

7.2. Safety Population

The safety population will include all subjects who received at least 1 dose of study treatment (KRP-A218, Itraconazole, or Placebo).

7.3. Pharmacokinetic Population

The PK population will include all subjects who received at least 1 dose of active study treatment (KRP-A218 or Itraconazole) and have at least 1 valid PK concentration.

7.4. Pharmacodynamic Population

The PD population will include all subjects who received at least 1 dose of study treatment (KRP-A218, Itraconazole, or Placebo) and have at least 1 valid postdose PD assessment.

